12. STUDY TREATMENT AND CONCOMITANT MEDICATIONS

Unless otherwise specified, analyses will be carried out in a descriptive manner using appropriate statistics as described in Section 6.1. Results will be provided by arm; no result on the pooled data across the two arms will be provided.

12.1. STUDY TREATMENT (PLACEBO, DUPILUMAB)

Analyses will be based on data recorded on eCRF form. Analyses will be carried out on the ITT population.

A study treatment administration is considered as actually received if the associated reported total dose is greater than 0.

12.1.1. Placebo

Analysis of Placebo exposure will include the following:

- Number and percentage of patients who received Placebo, regardless of the amount administered.
- Total number of administrations of Placebo actually received, regardless of the amount administered (quantitative parameter and qualitative parameter: "0", "1", "2", "3", "4").
- Received cumulative dose of Placebo in ml (quantitative parameter).
 Received cumulative dose of Placebo (in ml) will be derived as the sum of the reported actual total doses received of Placebo during the different injections.
- Number and percentage of patients with at least one dose reduction/suppression of Placebo, overall and by reason for dose reduction/suppression (that is, "Due to adverse event", "Due to other than adverse event"; as reported by investigators). Of note, a patient can be counted in more than one reason for dose reduction/suppression since as per protocol nine administrations (including two on the first visit) of Placebo have to be received by patient.

Tabulated individual data listing will be further provided; listing will include arm as randomly assigned to by the randomization system, arm as actually received, and all study treatment administration data (Placebo and Dupilumab).

12.1.2. Dupilumab

Analysis of Dupilumab exposure will include the following:

- Number and percentage of patients who received Dupilumab, regardless of the amount administered.
- Total number of administrations of Dupilumab actually received, regardless of the amount administered (quantitative parameter and qualitative parameter: "0", "1", "2", "3", "4").
- Received cumulative dose of Dupilumab in ml (quantitative parameter).
 Received cumulative dose of Dupilumab (in ml) will be derived as the sum of the reported actual total doses received of Placebo during the different injections.
- Number and percentage of patients with at least one dose reduction/suppression of Dupilumab, overall and by reason for dose reduction/suppression (that is, "Due to adverse event", "Due to other than adverse event"; as reported by investigators). Of note, a patient can be counted in more than one reason for dose reduction/suppression since as per protocol nine administrations (including two on the first visit) of Dupilumab have to be received by patient.
 - Tabulated individual data listing will be further provided; listing will include arm as randomly assigned to by the randomization system, arm as actually received, and all study treatment administration data (Placebo and Dupilumab).

12.2. CONCOMITANT MEDICATIONS

Concomitant medications will include those medications recorded on "Concomitant treatment" eCRF forms and which were received between the first study treatment administration (included) and the last study treatment administration (included).

A medication is defined as being received between the first study treatment administration (included) and the last study treatment administration (included) if:

- Its start date is between the date of the first study treatment administration (included) and the date of the last study treatment administration (included), regardless of its end date.
- Or, its start date is prior to the date of first study treatment administration and its end date is after or equal to the date of first study treatment administration.

In case of completely missing or incomplete medication start date (respectively medication end date), imputed start date (respectively end date), applying imputation rules as defined in Section 6.3.10, will be used to classify in any case medication as concomitant medication or not.

Number and percentage of patients who received concomitant medication(s) will be summarized by arm in the ITT population, and overall.

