- Treatment with oral immunosuppressants (including cyclosporine, methotrexate, azathioprine, mycophenolate mofetil), alitretinoin or phototherapy within 4 weeks of baseline visit.
- Treatment with an investigational drug within 8 weeks (or 5 half-lives) of baseline.
- Active chronic infection requiring the use of a systemic antibiotic within 2 weeks before study start.
- Known or suspected history of immunosuppression, including history of invasive opportunistic infections (e.g., tuberculosis, histoplasmosis, listeriosis, coccidioidomycosis, pneumocystis, aspergillosis) despite infection resolution; or unusually frequent, recurrent, or prolonged infections, per investigator judgment.
- History of human immunodeficiency virus (HIV) infection or positive HIV serology at screening.
- Positive for hepatitis B surface antigen, hepatitis B core antibody, or hepatitis C antibody at the screening visit.
- Patients with known helminth infections.
- Pregnant or breastfeeding women, or women planning to become pregnant or breastfeed during the study.
 Women of childbearing potential who are sexually active and unwilling to use an adequate birth control method.

After confirmation of eligibility, patients are randomly allocated by a computer-generated randomization system in a 1:1 ratio to receive one of the following two treatment strategies:

- Dupilumab 300 mg for subcutaneous administration. Two initial injections of 300 mg dupilumab will be administered, followed by one injection of 300 mg every 2 weeks until week 14.
- Placebo with the same administration procedure.

The randomization is performed in a stratified manner based on the presence or not of a personal history of atopic dermatitis, as it is expected to be the major factor potentially influencing the primary endpoint. Baseline severity is not expected to influence the primary endpoint, as the relative change in mTLSS is not anticipated to be influenced by disease severity.

After randomization, study treatment is begun as soon as possible.

Some treatments/procedures are prohibited during the study as either they may influence disease outcome or may pose a safety risk for patients. Treatment with the following concomitant medications is prohibited during the study

- Treatment with immunomodulating biologics.
- Treatment with an investigational drug (other than dupilumab).

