7.2. PP POPULATION

The Per-Protocol (PP) population consists of patients from the ITT population who are assessable for the primary endpoint and are deemed not to have major protocol deviations.

Patients will be analyzed as members of the arm corresponding to the study treatment they actually received that is, as soon as a patient receives dupilumab as part of study, he/she will be analyzed in dupilumab Arm; on the contrary, a patient who never receives dupilumab as part of study, will be analyzed in placebo Arm.

The PP population will be used as a supportive set of patients for the efficacy analysis to investigate the sensitivity of the conclusions drawn from the analyses of the primary endpoint carried out on the ITT population.

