- Poor compliance to placebo treatment; that is, administration of more or less than 9 injections (18ml) during the different study visits. Determination of the non-compliance will be done by programming using data related to study treatment administrations.
- Irregularities in time between visit/injection dates:
 - Scheduled visit/injection dates vary by plus or minus 3 days from the expected date.
 Determination of the non-compliance will be done by programming using data related to visit/injection dates.
 - The scheduled date for visit at V9 (16 weeks from the date of randomization (V1)) differs by plus or minus 24 days from the expected date.
 Determination of the non-compliance will be done by programming using data related to the V1 date and the V9 date.

- Lack of efficacy measurements:
 - No primary endpoint assessment; that is, no mTLSS score at week 16 available.
 Determination of the lack of efficacy measurements will be done by programming using data related to mTLSS assessments.
- Concomitant therapy/medication restrictions not followed:
 - o Intake of non-protocol therapy during the study; that is, intake, between day of randomization (included) and day of assessment to week 16 of mTLSS. Non-protocol therapies prohibited during the study are:
 - Treatment with immunomodulating biologics
 - Treatment with an investigational drug (other than dupilumab)
 - Treatment with topical corticosteroids or topical calcineurin inhibitors; such agents should not be administered during the study.
 - Treatment with systemic corticosteroids or non-steroidal systemic immunosuppressive drugs (e.g., cyclosporine, methotrexate, mycophenolate-mofetil, azathioprine, etc.), except if critically medically needed to treat concurrent medical conditions (e.g., asthma).

Study drug will be temporary discontinued (5 half-life before and after vaccination) if a treatment with live (attenuated) vaccine is used through week 16.

In addition, major surgery procedure and phototherapy (medical device or tanning) are prohibited during the 16-week treatment period.

Rescue therapy: if a patient presents with a severe flare of CHE during the course of the study which cannot be managed with emollients and requires intervention, a unique rescue 2-week course of highly potent corticosteroid (betamethasone dipropionate cream) will be administered. The amount of drug used will be recorded. Study treatment will be unchanged.

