8.2.2. Exclusions from the PP population

Criteria for a randomized patient to be excluded from the PP population are those major criteria of non-adherence to study protocol, that may be likely to affect the assessment of the primary endpoint. These criteria are as follows:

- Patients who are not evaluable for primary endpoint
- Patients who do not meet the diagnosis criteria for hand dermatitis
- Patients with only mild disease at baseline (IGA<3)
- Patients with a treatment dose not in line with the expected dose (9 injections)
- Time difference between V1 and V9 not included between \pm 24 days compared to the expected duration
- Patients using systemic immunosuppressant, including oral corticosteroids, through week 16
- Patients with a severe flare of CHE using highly potent corticosteroid (betamethasone dipropionate cream) as rescue therapy for more than 2-week, through week 16.

Inhaled/nasal corticosteroid for asthma, rhinitis or chronic obstructive pulmonary disease will be considered as authorized treatment.

Intra articular corticosteroid injection and topical corticosteroids not applied to the hands will be considered

as minor protocol violation.

Patients with a major protocol violation will be listed during the Blind Review.

Number and percentage of patients excluded from the PP population will be summarized overall and by exclusion criterion on the ITT population. Results will be provided on the pooled data across the two arms and by arm.

Tabulated individual data listing will be provided for those patients excluded from the PP population; listing will include the reason(s) for being excluded from the PP population.

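### The concomitant-medication window (12.2) stops at the last injection rather than the week-16 mTLSS, and the per-protocol exclusions (8.2.2) do not match the prohibited treatments in 8.1

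*SAP*

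**What the plan says.** **Reporting window.** SAP 12.2 defines concomitant medications as those "which were received between the first study treatment administration (included) and the last study treatment administration (included"). A medication qualifies if it starts between the first administration and "the date of the last study treatment administration (included), regardless of its end date", or if it started before the first administration and had not ended by then. The planned output is one line: "Number and percentage of patients who received concomitant medication(s) will be summarized by arm in the ITT population, and overall". Section 5.1 sets the schedule: two initial injections, then "one injection of 300 mg every 2 weeks until week 14". The primary endpoint (5.2.1) is at week 16.

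**Deviation window.** SAP 8.1 looks for prohibited therapy over a different period: "intake, between day of randomization (included) and day of assessment to week 16 of mTLSS". Sections 5.1 and 8.1 also allow one two-week rescue course of betamethasone cream and state that the amount used is recorded.

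**Per-protocol list.** Two criteria in 8.2.2 concern treatments other than the study drug. One removes users of systemic immunosuppressants, including oral corticosteroids. The other removes patients with a severe flare "using highly potent corticosteroid (betamethasone dipropionate cream) as rescue therapy for more than 2-week, through week 16". As minor violations it names intra-articular injections, while "topical corticosteroids not applied to the hands will be considered" the same way.

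**Wrong product.** Section 8.1 lists this as a dosing irregularity. Section 8.2.2 does not name it, and 7.2 assigns per-protocol patients by product received: "as soon as a patient receives dupilumab as part of study, he/she will be analyzed in dupilumab Arm".

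**The concern.** Topical steroids and calcineurin inhibitors act on the lesions that the mTLSS scores, so a reader of the trial report will want to know who used them on the hands, when and how much.

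The table that should answer this stops short of the endpoint. The part it omits is the part closest to the assessment, when an active course matters most.

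The per-protocol analysis is one of three sensitivity analyses of the primary endpoint (13.1.3). Its exclusion list leaves several prohibited treatments unclassified. Unless the list is completed, each such patient has to be decided case by case or is kept by default. What is at stake is how the week-16 result is interpreted and what the supportive population means. The primary test itself is not at stake.

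**Working it through.** **Step 1: reproduce the schedule.** Inputs are from 5.1, 8.1 and 12.1. Two injections at the start plus one at each of weeks 2, 4, 6, 8, 10, 12 and 14 gives 2 + 7 = 9 injections. At 300 mg each, 9 × 300 = 2700 mg, which is the figure in 8.1. The last planned injection is therefore at week 14.

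**Step 2: size of the gap between 12.2 and 8.1.**
- On schedule: (16 − 14) × 7 = 14 days, or 14/112 = 12.5% of the 16 weeks.
- With visit 9 at the later edge of the 24-day tolerance and the last injection on time: 14 + 24 = 38 days.
- With early cessation of injections at week w and follow-up continued, which 5.1 foresees: (16 − w) × 7 days. For example, w = 8 gives 56 days.

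The on-schedule gap equals the length of the permitted rescue course. A course begun the day after the last injection could still be in use at the week-16 mTLSS and would not appear in the 12.2 table. A course begun on or before the day of the last injection does appear, whatever its end date.

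**Step 3: is the missing information shown elsewhere?**
- Section 12.2 plans only the count of patients with any concomitant medication. Any ATC tables implied by the sorting rules in 6.4 would use the same window.
- Section 8.1 describes how deviations are determined but plans no table of them by arm.
- Section 8.2.2 tabulates exclusions by criterion and by arm. That shows rescue beyond two weeks and nothing shorter.
- The rescue amount is recorded (5.1, 8.1), but no section summarises it.

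**Step 4: set 8.1 against 8.2.2.**

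| Prohibited or irregular under 8.1 | Treatment in 8.2.2 |
|---|---|
| Systemic corticosteroids, systemic immunosuppressants | Systemic immunosuppressants and oral corticosteroids excluded, through week 16 |
| Betamethasone rescue beyond the permitted course | Excluded if over 2 weeks, through week 16 |
| Topical steroids off the hands | Minor violation |
| Topical steroids on the hands, outside rescue | Not classified |
| Topical calcineurin inhibitors | Not named |
| Immunomodulating biologics | Not named; whether they count as systemic immunosuppressants is undefined |
| Other investigational drugs | Not named |
| Phototherapy | Not named |
| Wrong product received | Not named; arm reassigned by 7.2 |

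**Step 5: wrong product.** A patient who receives nine injections of the other product meets the nine-injection criterion, is not otherwise excluded, and is analysed in the other arm. A patient with a mixture of products is less clear, because 8.1 counts the nine injections per product and such a patient may fail the dose criterion. The point is therefore limited to a full course of the wrong product.

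**Step 6: direction of any effect on the estimate.** Let r be the excess proportion of placebo patients using hand steroid near week 16, and g the extra improvement each gains. The difference of 25 points assumed in 5.3 becomes 25 − r × g, which is smaller whenever r and g are positive. The SAP gives neither r nor g, so only the direction is stated here.

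**The case against.** The strongest reply is that 12.2 is a descriptive table that feeds no efficacy analysis, and that a table of medication taken alongside study drug may reasonably have a different window from a deviation check. This is largely right. A reader might infer that the short window lets steroid users slip into the per-protocol set. The SAP does not support that: 8.1 works from the medication data up to the week-16 mTLSS, and both drug criteria in 8.2.2 run through week 16. A patient who stops injections early also fails the nine-injection criterion. The two inconsistencies are separate.

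On the per-protocol set, keeping patients who used the one permitted two-week course is coherent, and longer rescue is already removed. The definition in 7.2 (no major deviations), the wording that calls only off-hand steroid use minor, and the Blind Review leave room to exclude hand users. So the text is ambiguous; it does not plainly retain them. The ambiguity still needs resolving, because 8.2.2 presents its criteria as the list to apply and a programmer would follow it.

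A reader might also infer that steroid use is a rival explanation for a positive result, or that the trial loses power. Neither follows. Rescue that is commoner on placebo shrinks the difference, which is conservative for a superiority claim. Any power figure would need usage rates and gains that the SAP does not give. Rescue is part of the design, so the planned 25 points may already allow for it, and no change proposed here alters the primary ITT analysis.

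**Conclusion.** The point holds as two modest but real inconsistencies that should be corrected.

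- The concomitant-medication table misses courses started in the last 14 days on schedule. The gap reaches 38 days with a visit 9 at the tolerance limit, and is longer after early cessation of injections. Rescue amount is collected but not reported.
- The per-protocol list leaves hand-applied steroids outside rescue unclassified. It does not name topical calcineurin inhibitors, biologics, other investigational drugs or phototherapy, and it moves a fully swapped patient to the other arm.

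The gap sizes rest only on the SAP's own schedule and tolerance. The expected direction of bias (dilution) rests on the assumption that rescue is commoner on placebo. No size is attached to that bias, and no loss of power is claimed.

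**What to change.** - **12.2:** extend the window to the date of the visit 9 mTLSS. Add a table by arm of rescue use and of prohibited hand treatment, with number of patients, timing relative to visit 9, and recorded amount of rescue cream. In the same edit, point the date-imputation reference to 6.3.11 (medications) instead of 6.3.10 (adverse events).
- **8.2.2:** before unblinding, go through the prohibited treatments in 8.1 one by one and state that use through visit 9, outside the permitted rescue course, excludes from the per-protocol set. Name hand-applied topical steroids, topical calcineurin inhibitors, immunomodulating biologics, other investigational drugs and phototherapy. Off-hand topical steroids can stay minor, as now.
- **7.2 and 8.2.2:** exclude patients who received the wrong product from the per-protocol set instead of moving them. The as-treated rule for safety (7.3) need not change.
- **Optional:** one further analysis with mTLSS after rescue set to missing and handled by the multiple imputation in 6.3.5. It answers a different question (the outcome had rescue not been used), so it is a choice for the sponsor and not a correction.

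The cost is SAP wording, one extra table and a slightly smaller per-protocol set. The classification should be fixed before unblinding, since deciding it with allocation known would undermine the supportive analysis.

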13. EFFICACY ANALYSIS

13.1. PRIMARY EFFICACY ENDPOINT

13.1.1. Definition and derivation

The primary efficacy endpoint is the percentage change in mTLSS score from baseline to Week 16 (quantitative parameter with one decimal place). It is calculated as follows:

$$\frac{\text{mTLSS score at visit 9 - mTLSS score at visit 1}}{\text{mTLSS score at visit 1}} \times 100$$

Missing data for this criterion will be imputed as described in section 6.3.5 for this analysis.

13.1.2. Primary analysis

Primary analysis of the primary efficacy endpoint will be carried out on the ITT population, using an adjusted approach controlling for those factors on which the randomization is stratified and on the value of the baseline endpoint.

Levels of factors on which the randomization is stratified will be derived from actual data - that is, last investigator eCRF data entry - to compensate for cases where erroneous stratification factor information were given at the time of randomization leading to randomization in a wrong stratum; see Section 8.1 for details of randomization irregularities.

Percentage change in mTLSS score from baseline to week 16 will be compared between Arm A and Arm B using a covariance analysis (ANCOVA) including the group, the stratification factor, the baseline mTLSS score, and the interaction between the treatment arm and the stratification factor as covariables. Initially, a bivariate test will be conducted between the variable to be explained (percentage change of mTLSS) and the treatment arm. The choice of the test will be based on classical criteria such as normality and homoscedasticity. Subsequently, an Analysis of Covariance (ANCOVA) will be performed. If the interaction is not significant ($p\geq0.05$), it will be excluded from the model. Otherwise, the analysis will be stratified based on the stratification factor.

Finally, we will verify if the conditions for applying ANCOVA are met by examining the distribution of the residuals graphically (normality and homoscedasticity).

In case all assumptions are not met, we will proceed with a linear regression using the same variables as the previous model but employing a more robust approach (10–12) that tolerates heteroscedasticity.

The null hypothesis H_0 is that percentage change in mTLSS score of Arm A is the same as percentage change in mTLSS score of Arm B after adjustment for stratification factor and the baseline score. The alternative hypothesis H_a is that percentage change in mTLSS score of Arm A differs as percentage change in mTLSS score of Arm B after adjustment for stratification factor and the baseline score.

The percentage change based on the treatment arm will be presented as the difference between the percentage change in arm A and the percentage change in arm B after adjustment. It will be presented with its 95% confidence interval (95% CI) constructed using the estimator of the standard variance for ordinary least squares (OLS) regression if the aforementioned hypotheses are met. Otherwise, this confidence interval will be provided using the robust standard errors described by Eicker-Huber-White (10–12) for heteroskedastic models. Finally, the predicted values per treatment group and their difference will be presented with their 95% CI.

These data will be presented in a table such as the one below:

Percentage change in mTLSS	N	β Coefficient	β 95% CI	p-value
Treatment arm				
Placebo	n	0		
Dupilumab	n	eta_1	$(CI_1;CI_{1'})$	p_1
Randomization stratum				
Presence of a personal history of atopic dermatitis				
No	n	0		
Yes	n	eta_2	$(CI_2;CI_{2'})$	p_2
mTLSS score at inclusion	n	β_3	(CI ₃ ; CI _{3'})	p_3
Other qualitative parameter of interest				
Modality 1	n	0		
Modality 2	n	eta_4	$(CI_4;CI_{4^{\text{'}}})$	p_4
Modality 3	n	eta_5	$(CI_5;CI_{5'})$	p_5
Other quantitative parameter of interest	n	eta_6	$(CI_6;CI_{6'})$	p_6
R - squared	R^2			

Percentage change in mTLSS	Mean predicted values	95% CI
Treatment arm		
Placebo		(CI; CI)
Dupilumab		(CI; CI)
Dupilumab - Placebo		(CI; CI)

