5.3. DETERMINATION OF SAMPLE SIZE

The sample size is determined by the primary objective of the study, that is, to compare the percentage change in mTLSS score from baseline to Week 16.

His calculations are based on a clinically meaningful absolute difference between groups in the mean percentage change in mTLSS score from baseline to Week 16 of -25% (greater percentage decrease expected in dupilumab compared with placebo). Assuming a standard deviation of 40% in both groups, sample size of 84 patients (42 by group) will achieve over 80% power to detect such a difference with a significance level (type-I error) of 0.05 using a two-sided two-sample t-test (7).

To account for potential non-evaluable patients estimated to 10%, a total of 94 patients will have to be randomized.

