6.2. INFERENTIAL STATISTICS

The primary objective of study is to demonstrate that dupilumab is more effective than placebo for the treatment of patients with moderate to severe CHE who are resistant or intolerant to highly potent topical corticosteroids as determined by the evolution at week 16 of the mTLSS since baseline. The study is sized on the basis of the primary objective only. The study uses a single primary endpoint and has a confirmatory statistical strategy that pre-specifies just one single null hypothesis relating to the primary endpoint and no formal interim analysis.

The primary analysis of the primary endpoint, which forms the basis for the sample size justification, involves comparing the percentage change from baseline to week 16 of the severity score mTLSS between the experimental arm (dupilumab) and the control arm (Placebo) using a covariance analysis. This analysis includes the group, the stratification factor (personal history of atopy), the baseline mTLSS score and the interaction between the stratification factor and the treatment arm as covariables. The treatment effect is tested at a 5% significance level.

The null hypothesis H_0 is that the percentage change in experimental arm is the same as the percentage change in control arm. The alternative hypothesis H_a is that percentage change in experimental arm differs from percentage change in control arm.

All other analyses of the other efficacy endpoints, are intended to yield supportive evidence related to the primary objective and to provide additional characterization of treatment effects, and no claims are intended. Confidence Intervals (CIs) and statistical tests, if any, that are part of these analyses are of exploratory nature and will be performed without any adjustment of type I error. They will be two-sided and performed each at the 0.05 significance level, unless otherwise specified.

Similarly, analyses on safety endpoints are used in an exploratory manner. CIs and statistical tests, if any, will be two-sided and performed each without any adjustment for multiplicity at the 0.05 significance level.

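### The primary test switches to stratum-specific analyses when an interaction pre-test has p<0.05, and no rule links two stratum results to the single hypothesis declared

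*SAP*

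**What the plan says.** Section 6.2 describes a confirmatory strategy that "pre-specifies just one single null hypothesis relating to the primary endpoint" and adds: "The treatment effect is tested at a 5% significance level". It lists the model terms as group, stratification factor, baseline mTLSS and "the interaction between the stratification factor and the treatment arm as covariables".

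Section 13.1.2 sets out the procedure:

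- A comparison of the arms comes first: "Initially, a bivariate test will be conducted between the variable to be explained (percentage change of mTLSS) and the treatment arm". The test is chosen on normality and homoscedasticity.
- The ANCOVA with the same four terms follows. If the interaction has p≥0.05 it is removed.
- If it does not: "Otherwise, the analysis will be stratified based on the stratification factor".

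The null hypothesis in 13.1.2 is one overall difference between arms, adjusted for stratum and baseline score. The results table has a single row for the dupilumab-minus-placebo difference. Nothing says how two stratum-specific results would be combined into a conclusion on the primary objective.

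**The concern.** The hypothesis that is tested depends on the data. When the interaction is significant, the plan gives up the overall adjusted comparison for which the hypothesis is stated and the trial was sized, and replaces it with two comparisons. It does not say whether one significant stratum is enough, whether both are needed, or whether the primary objective is then left without a formal answer. That choice would be made after unblinding, with the results in view.

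The branch is not remote. Section 5.1 expects history of atopic dermatitis to be the main factor influencing the primary endpoint, and section 6.3.5 imputes by arm because it allows for an interaction between stratum and arm.

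**Working it through.** **1. The plan's own figure.** Inputs from section 5.3: difference 25 points, SD 40, two-sided 5%, two-sample t-test, 84 evaluable patients (42 per arm), 10% non-evaluable.

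- Standardised effect: 25/40 = 0.625.
- The t-test solution for 80% power is 41.17 per arm, rounded up to 42. Power at 42 per arm is 0.808.
- 84/0.90 = 93.3, rounded up to 94.

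The sample size reproduces and is not in question.

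**2. False-positive rate of the written rule.** Assume no effect in either stratum. Let Z1 and Z2 be the independent standard normal statistics for the two strata, and f the share of patients in the larger stratum. The SAP gives no prevalence, so f is an assumption.

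- Interaction statistic: I = (Z1/√f − Z2/√(1−f)) / √(1/f + 1/(1−f)).
- Overall statistic: O = Z1√f + Z2√(1−f).

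I and O are orthogonal contrasts, so the pre-test and the overall test are independent under the null:

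Error = P(interaction p≥0.05) × 0.05 + P(interaction p<0.05) × P(success declared | interaction p<0.05)
= 0.95 × 0.05 + 0.05 × q = 0.0475 + 0.05q.

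The SAP does not determine q. From 20 million draws for each f:

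| What counts as success in the stratified branch | Total error |
|---|---|
| No claim (q = 0) | 4.75% |
| Both strata p<0.05 | about 4.9% |
| Either stratum p<0.05, f = 50% (q = 0.65) | 0.0475 + 0.0325 = 8.0% |
| Either stratum, f = 70% (q = 0.68) | 8.1% |
| Either stratum, f = 80% (q = 0.71) | 8.3% |

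Full ANCOVA simulations under the either-stratum reading (40,000 trials each, N = 84 and 94, f from 50% to 80%) gave 7.6% to 8.1%. In the same runs a main-effects ANCOVA that is always tested gave 4.9% to 5.2%.

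**3. How often the branch is entered.**

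- Equal effects in the two strata: about 5% of trials, by construction.
- Illustration with true effects of -10 and -40 in equal strata (mean -25), N = 84, so 21 patients in each arm-by-stratum cell: SE of the interaction = 40 × √(4/21) = 17.5; 30/17.5 = 1.72; P(Z > 1.96 − 1.72) ≈ 0.40. In about 40% of trials the plan would then specify no adjusted overall test.

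**4. Power at the planned effect.** With -25 in both equal strata and N = 84, the fixed main-effects ANCOVA has 81.1% and the written rule, read as either stratum, 82.0%.

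**The case against.** Several points on the other side stand.

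- A reader might infer that the 5% error simply becomes 8%. The SAP does not say that one significant stratum would suffice. It keeps one overall hypothesis and one overall difference in the table, which fits just as well with making no claim in that branch, and then the error stays just below 5%. The 8% is conditional on a rule that is not written down.
- A reader might infer that the overall effect may never be tested. The preliminary bivariate comparison of the arms is run in every case, so only the adjusted test is lost. This does not rescue the plan: the comparison is unadjusted, its form is chosen from the data, and section 6.2 names the covariance analysis as primary. Counting it as a further route to success, on top of the either-stratum reading, gives 8.0% to 8.5% in simulation.
- A reader might take section 6.2 as a separate procedure that keeps the interaction and tests the effect in the reference stratum. It names the same four terms as the starting model in 13.1.2, which then says how the interaction is handled. The interaction is either dropped or the analysis is split, so that coefficient is never the deciding test.
- The table row labelled "Other qualitative parameter of interest" might be read as leave to add covariates. The table is given as an example layout, and both sections list the covariates. The pre-specified fallback to robust standard errors is a separate matter, and nothing here shows that it does harm.
- The written rule does not lose power when effects are equal, as step 4 shows.

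What the objection leaves untouched is that the significant-interaction branch has no decision rule.

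**Conclusion.** The point holds as a contradiction within the SAP. Section 6.2 and the hypothesis in 13.1.2 declare one overall adjusted test at 5%; the procedure in 13.1.2 can replace it with two stratum analyses and no rule for a single conclusion. The defect is that the error rate and the basis for the primary conclusion are left open, not that the error is known to be inflated. Under no effect the rate runs from about 4.7% to about 8.3%, depending on the unstated rule and on an assumed larger-stratum share of 50% to 80%. The 40% entry figure rests on illustrative effects that the SAP does not give. Because this concerns the trial's only confirmatory test, it should be settled before unblinding.

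**What to change.** In sections 6.2 and 13.1.2, name one primary test: ANCOVA of percentage change in mTLSS on arm, stratification factor and baseline mTLSS, without interaction, with the arm coefficient tested two-sided at 5% whatever the interaction p-value. Report the interaction test and the stratum-specific estimates with confidence intervals as exploratory, and label the bivariate comparison descriptive. The sensitivity analyses in 13.1.3 refer back to the primary analysis and would follow the same model.

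The cost is SAP wording. A strong interaction would be reported only as exploratory. Power at the planned effect is about 81%, roughly one point below the written rule under the either-stratum reading, and the error returns to 5%.
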